6.4.30. Permitted Medications

Permitted medications include, but are not limited to:

- Doses of oral aminosalicylate, probiotics, or antibiotics prescribed for CD should be stable during the Screening and Induction, after which dose may be adjusted up or down during ATE or during the 4 weeks between last dose of study drug and EOS visit.
- Oral corticosteroids for CD are permitted at a stable dose ≤ 25 mg/day of prednisone or beclomethasone 5 mg/day or equivalent or ≤ 9 mg/day budesonide during Day 1 through Week 12 but need to start to be tapered slowly at Week 8. The required tapering regimen is as follows: prednisone (or equivalent) dose should be tapered by 2.5 mg/day every week until completely off by ATE Week 6. If subject is on budesonide, budesonide MMX, or beclomethasone, then the dose should be tapered according to clinical practice. Oral, topical, or intranasal corticosteroids for non-CD indications are permitted during ATE.

- The only rescue medication permitted (i.e., that allows subjects to stay in the study and continue study drug) is the addition or increase in oral corticosteroid dose up to or above the dose at baseline.
 - If a subject requires one increase of the corticosteroid dose up to baseline dose (defined as dose at Day 1) during the taper, he/she can continue study as usual.
 - If subject requires during Induction a) use of a higher corticosteroid dose than the baseline dose, or b) de novo initiation of corticosteroids of any route of administration for CD symptoms, the subject can continue study drug (but may be deemed as meeting treatment failure definition). The subject would need to taper the steroid dose within two weeks after initiation using the tapering regimen as outlined above.
 - If subject requires during ATE a) use of a higher corticosteroid dose than the baseline dose, or b) de novo initiation of corticosteroids of any route of administration for CD symptoms after ATE Week 16, the subject should discontinue study drug treatment and return for an EOS Visit. For those who initiate or increase corticosteroid dose before ATE Week 16, consider tapering the steroids within two weeks after initiation using the tapering regimen as outlined above.
- Addition of, cessation of, or dose adjustments for the following are allowed during the study:
 - Hormonal therapy for postmenopausal females
 - Oral contraception for females of childbearing potential
 - Aspirin for cardio protection at a maximum dose of 325 mg/day
- Any medication used on a long-term basis at a stable dose (e.g., oral contraceptive pill, multivitamins); doses of non-CD prescription and over-the-counter medications may be altered or new medications may be added during the study only if they are medically indicated and do not confound safety assessment, as deemed by the investigator or Medical Monitor; however, such changes should be minimized during Weeks 1-12.

6.4.31. Restrictions on Alcohol Consumption and Illicit Drug Use

Alcohol or illicit drug abuse, per the judgment of the investigator, within 1 year of Screening until the EOS visit is not allowed.

6.5. Discontinuation

6.5.1. Subject Discontinuation

Any subject may withdraw their consent to participate in the study at any time without prejudice. The investigator must withdraw from the study any subject who requests to be withdrawn. A subject's participation in the study may be discontinued at any time at the discretion of the investigator and in accordance with his or her clinical judgment.

When possible, the tests and evaluations listed for the Early Study Drug Discontinuation visit and EOS visit should be carried out, as noted in Sections 6.3.12 and 6.3.15. If a subject withdraws before completing the study, the reason for withdrawal is to be documented on the CRF.

The Sponsor will be notified of all subject withdrawals.

Reasons for which the investigator or the Sponsor may withdraw a subject from the study or a subject may choose to terminate participation before completion of the study include the following:

- Adverse event
- Subject choice / Withdrawal of consent
- Major violation of the protocol
- Termination of the study by the Sponsor
- Need for a new prohibited medication for CD or surgery
- Lost to follow-up
- Subject demonstrates lack of clinical benefit (e.g., ATE Week 16 visit)
- Pregnancy
- Other

Subjects with laboratory abnormalities must recheck lab values or discontinue study drug as outlined in Section 7.2. Any non-laboratory-related AE considered an AESI defined in Section 7.1.4, except for non-melanoma skin cancer, should also lead to study drug discontinuation. Subjects who discontinue study drug early because of an adverse reaction should be encouraged to continue their participation in the follow-up safety assessments. If a subject fails to return for scheduled visits, a documented effort must be made to determine the reason.

6.5.2. Subject Replacement

At the Sponsor's discretion, subjects who withdraw or are withdrawn before taking study drug may be replaced. Should greater than 10% of treated patients withdraw before the primary endpoint visit or miss the primary endpoint visit due to events that could not be foreseen during study design planning (e.g., COVID-19 pandemic) then treated subjects may be replaced. Safety data will be presented for all subjects in the Clinical Study Report (CSR) regardless of whether the subject was a replacement.

6.5.3. Study Discontinuation

The Sponsor reserves the right to discontinue this study at any time for any reason. Periodic review of unblinded safety data by an external Independent Data Monitoring Committee (IDMC) (Section 8.10) may lead to the board's recommendation of pausing dosing or terminating the study. In the event of premature study termination, best efforts to guarantee appropriate safety follow-up of subjects who have already been enrolled will be made and IRBs and the Regulatory Authorities will be informed.

6.6. Pregnancy

If a female subject becomes pregnant during the study from the time of consent until 7 days after the subject's last dose of study drug, the Sponsor Clinical Study Director (or designee) must be notified immediately, and study drug discontinued if subject is still on study drug treatment.

Follow-up information regarding the outcome of the pregnancy and any postnatal sequelae in the infant will be required. If the partner of a male subject becomes pregnant during the study from the time of consent until 7 days after the subject's last dose of study drug, the Sponsor's Clinical Study Director (or designee) must be notified immediately. Follow-up information regarding the outcome of the pregnancy and any postnatal sequelae in the infant will be required.

All pregnancies whether of a subject participating in the study or in the female partner of a male subject in the study should be reported within 24 hours of awareness using the Pregnancy Notification Form.

7. ADVERSE EVENTS

7.1. Definitions

The definitions below are based on International Conference on Harmonization (ICH) guideline E2A, “Clinical Safety Data Management: Definitions and Standards for Expedited Reporting”.

7.1.1. Adverse Events (AE)

An AE is any untoward medical occurrence in a patient or clinical trial subject administered a pharmaceutical product that does not necessarily have to have a causal relationship with this treatment. An AE can therefore be any unfavorable and unintended sign (including an abnormal laboratory finding), symptom, or disease temporally associated with the use of a medicinal product, whether or not related to the medicinal product.

- AEs may be new events
- Preexisting events that increase in frequency, severity or change in nature or seriousness during or as a consequence of participation in clinical studies.
- Pre- or post-treatment complications that occur as a result of a protocol-mandated procedure (such as a biopsy).
- AEs may be clinically significant changes from baseline in physical examination, laboratory tests, or other diagnostic investigation (e.g., laboratory results, x-ray findings).
- AEs may result from an overdose of the study medication.

Whenever possible, the diagnosis (rather than a series of terms related to a diagnosis) should be recorded as the AE term.

An AE does not include the following:

- Medical or surgical procedures (such as surgery, endoscopy, tooth extraction, or transfusion); the condition that leads to the procedure is an adverse event
- Preexisting diseases or conditions present or detected before signing an informed consent form that do not worsen
- Situations where an untoward medical occurrence has not occurred (such as hospitalization for elective surgery or social and/or convenience admissions)
- Overdose of either study drug or concomitant medication without any signs or symptoms, unless the subject is hospitalized for observation

Any medical condition or clinically significant laboratory abnormality with an onset date prior to the time the subject signed the informed consent form is considered to be preexisting and should be documented in the medical history CRF.

Pregnancy is not an AE; however, if a female subject becomes pregnant during the study from the time of consent until 7 days after the subject’s last dose of study drug, Theravance Biopharma, Inc. (TBPH) will be notified according to the procedures for SAE reporting as

outlined in Section 7.4.3. Follow-up information regarding the outcome of the pregnancy and any fetal or neonatal sequelae will be obtained and documented.

7.1.2. Serious Adverse Event

A serious adverse event (SAE) is defined as any untoward medical occurrence occurring at any dose that results in any of the following outcomes:

- Death
- Life-threatening situation. “Life-threatening” refers to a situation in which the patient was at risk of death at the time of the event; it does not refer to an event which might have caused death if it were more severe.
- Inpatient hospitalization or prolongation of existing hospitalization

Note: “Inpatient hospitalization” means the subject has been formally admitted to a hospital for medical reasons, for any length of time. This may or may not be overnight. It does not include presentation and care within an emergency department. A scheduled hospitalization for a preexisting condition that has not worsened during participation in the study does not meet this criterion. Pre-planned hospitalizations for an elective medical/surgical procedure, scheduled treatments, or routine check-ups do not meet this criterion. Complications that occur during hospitalizations are AEs. If a complication prolongs hospitalization, it is an SAE.

Disability. A persistent or significant incapacity or substantial disruption of the ability to conduct normal life functions

- Congenital anomaly/birth defect in the offspring of a subject who received study drug
- Important medical events that may not result in death, be immediately life-threatening, or require hospitalization, may be considered an SAE when, based upon appropriate medical judgment, they may jeopardize the subject and may require medical or surgical intervention to prevent one of the outcomes listed in this definition. Examples of such events are as follows:
 - Intensive treatment in an emergency room or at home for allergic bronchospasm
 - Blood dyscrasias or convulsions that do not result in hospitalization
 - Development of drug dependency or drug abuse

7.1.3. Additional Considerations for Serious Adverse Events

- Death is an outcome of an adverse event and not an adverse event in itself. Deaths of unknown cause for which the investigator cannot identify a cause of death will be captured as death of unknown cause or death not otherwise specified.
- All deaths, regardless of cause, must be reported for subjects if the death occurs while the subject is participating in the study.
- “Occurring at any dose” does not imply that the subject is receiving study drug at the time of the event; dosing may have been given as treatment cycles or interrupted temporarily before the onset of the SAE, but may have contributed to the event.

7.1.4. Adverse Events of Special Interest (AESIs)

At each study visit, the Investigator (or designee) will specifically query for any adverse events of special interest (AESIs). The following events are considered AESIs for this study:

- suspected or confirmed intestinal perforation
- complicated herpes zoster (multi-dermatomal, disseminated, or with ophthalmic or CNS involvement)
- malignancy excluding non-melanoma skin cancer
- non-melanoma skin cancer
- serious infection (e.g., that requires hospitalization or intravenous antibiotics)
- opportunistic infections
- thromboembolic disease (e.g., DVT, pulmonary embolism)
- clinical laboratory abnormalities of concern (Section 7.2)
- cardiovascular event (e.g., myocardial infarction or cerebrovascular accident)

All AESIs, except for non-melanoma skin cancers, must be reported to TBPH Clinical Safety and Pharmacovigilance within 24 hours of awareness by the Investigator or his/her designee (Section 7.4.3). Except for non-melanoma skin cancer that has been fully resected, mono-dermatomal herpes zoster, and certain laboratory abnormalities that are deemed by the investigator to not place subjects at immediate safety risk, all of these AESIs should lead to discontinuation of the study drug. For each of these AESIs, an additional targeted questionnaire needs to be completed to assess for risk factors. For thromboembolic events in particular, the subject should undergo evaluation for hypercoagulable state (e.g., with clinically relevant investigations, such as referral to a specialist and/or blood testing for a predisposition to a hypercoagulable state) and repeat imaging to assess resolution of the finding.

7.2. Clinical Laboratory Abnormalities and Other Abnormal Assessments as Adverse Events or Serious Adverse Events

Abnormal laboratory findings (such as clinical chemistry, hematology, or urinalysis) or other abnormal assessments (such as electrocardiograms [ECGs], X-rays, or vital signs) that are considered clinically significant in the judgment of the investigator may be recorded as AEs or SAEs if they meet the definition of an adverse event (or serious adverse event), as described in Sections 7.1.1 (Adverse Event) and 7.1.2 (Serious Adverse Event). Merely repeating an abnormal test does not constitute an adverse event. Any abnormal test result that is determined to be an error does not require reporting as an adverse event.

Clinical laboratory abnormalities of concern may include, but are not limited to, the following where the investigator must recheck within 2-7 days, as deemed appropriate by the investigator, except for AST or ALT > 3x ULN where these need to be rechecked within 48-72 hours:

- clinically significant reduction in leukocytes or leukocyte subsets that may place subjects at higher risk for infection such as:
 - moderate neutropenia (e.g., absolute neutrophil count of < 1.0 x 10⁹/L)

- moderate leukopenia (e.g., white blood cell count of $< 2.0 \times 10^9/L$)
- moderate lymphocytopenia (e.g., absolute lymphocyte count of $< 0.5 \times 10^9/L$)
- abnormal hepatic panel (AST or ALT) $> 3x$ ULN
- an excessive decrease in creatinine clearance (e.g., a reduction by $\geq 50\%$ from baseline, baseline for this purpose is defined as creatinine clearance calculated for Day 1, pre-dose)

Depending on the subject's baseline and individual scenario, the investigator should report as an AESI, and stop study drug treatment if any of the below is seen:

- moderate neutropenia (e.g., absolute neutrophil count of $< 1.0 \times 10^9/L$) on two sequential lab results
- moderate leukopenia (e.g., white blood cell count of $< 2.0 \times 10^9/L$) on two sequential lab results
- moderate lymphocytopenia (e.g., absolute lymphocyte count of $< 0.5 \times 10^9/L$) on two sequential lab results
- a reduction by $\geq 50\%$ from baseline in creatinine clearance on two sequential lab results
- Abnormal AST or ALT $> 3x$ ULN on two sequential lab results with associated bilirubin $> 2x$ ULN on at least one of the two lab results or international normalized ratio (INR) > 1.5 on at least one of the two reports (INR will need to be checked locally),
- ALT or AST $> 8x$ ULN **on a single lab result**
- AST or ALT $> 5x$ ULN on two sequential lab results at least 2 weeks apart, or
- AST or ALT $> 3x$ ULN **on a single lab result associated with signs or symptoms suggestive of acute liver injury** (e.g., the appearance of fatigue, nausea, vomiting, right upper quadrant pain or tenderness, fever, rash, and/or eosinophilia ($> 5\%$)).

[Appendix 12](#) presents an algorithm for evaluating and managing subjects with ALT or AST $> 3x$ ULN

The first occurrence of these laboratory abnormalities may not trigger the definition of an AESI and study drug discontinuation until the second sequential abnormality (except for the two bolded circumstances above). If there are any questions as to whether a laboratory abnormality should be reported as an AE or an AESI, the investigator is encouraged to contact the Medical Monitor to discuss.

7.3. Assessment of Adverse Events

All AEs will be assessed by the investigator and recorded in the case report form, including the dates of onset and resolution, severity, relationship to study drug, outcome, and action taken with study medication.

7.3.1. Severity

The term “severe” is often used to describe the intensity (severity) of a specific event (as in mild, moderate, or severe myocardial infarction); the event itself, however, may be of relatively minor medical significance (such as severe nausea). This is not the same as “serious,” which is based on patient/event outcome or action criteria usually associated with events that pose a threat to a subject’s life or functioning. The severity of AEs will be assessed according to the following definitions:

- **Mild:** the AE is noticeable to the patient and/or the Investigator, but does not interfere with routine activity.
- **Moderate:** the AE interferes with routine activity, but responds to symptomatic therapy or rest.
- **Severe:** the AE significantly limits the patient’s ability to perform routine activities despite symptomatic therapy.

7.3.2. Causal Relationship to Study Medication

The Investigator’s assessment of causality is based on clinical judgment regarding the reasonable possibility that the study medication caused the event and may include consideration of some or all of the following factors:

- Possible alternative causes of the AE, including the disease under treatment, co-morbid conditions, other drugs, and environmental factors.
- The temporal association between drug exposure and onset of the AE.
- Whether the clinical or laboratory manifestations of the AE are consistent with known actions or toxicity of the study medication.
- Whether the AE resolved or improved with decreasing the dose or stopping the study medication (“dechallenge”) or recurred or worsened upon re-exposure to the study medication (“rechallenge”).

The causal relationship between the study medication and the AE will be described using one of the following categories:

- **Not Related:** Evidence exists that the adverse event has an etiology other than the study drug (such as a preexisting condition, underlying disease, intercurrent illness, or concomitant medication).
- **Related:** A temporal relationship exists between the event onset and administration of the study drug. It cannot be readily explained by the subject’s clinical state or concomitant therapies and appears with some degree of certainty to be related based on the known therapeutic and pharmacologic actions of the drug. In case of cessation or reduction of the dose, the event abates or resolves and reappears upon rechallenge. It should be emphasized that ineffective treatment should not be considered as causally related in the context of adverse event reporting.

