7.4.3. SAE and AESI Reporting Timeline

SAEs and AESIs (except for non-melanoma skin cancer) will be reported to Clinical Safety and Pharmacovigilance within 24 hours of the time the Investigator or his/her designee becomes aware that a SAE or AESI has occurred, whether or not the event is considered to be related to study medication. If the initial SAE is reported by telephone, a written report signed by the Investigator must be submitted within 24 hours.

The SAE/AESI Report Form must be completed in accordance with the SAE/AESI Report Form Completion Guidelines. If all information on the SAE/AESI Report Form is not available at the time of the initial report, follow-up SAE/AESI reports will be completed and submitted.

To report an SAE or AESI, complete and fax or email the appropriate Case Report Form to the following:

Theravance Biopharma Clinical Safety and Pharmacovigilance

[REDACTED]

For medical questions regarding an SAE or an AESI, contact the Sponsor's medical monitor by telephone as follows:

Medical Monitor Contact Information:

[REDACTED]

For fatal or life-threatening events, also fax copies of hospital case reports, autopsy reports, and other documents when requested. Additional information may be requested from the investigator to ensure the timely completion of accurate safety reports.

An SAE may qualify for reporting to regulatory authorities if the SAE is possibly attributable to the study drug and is unexpected/unlisted based on the current TD-1473 Investigator's Brochure. In this case, all investigators will receive notification of the event. The investigator is responsible for notifying the Institutional Review Board or Ethics Committee and documenting the notification, as required by local regulatory authorities and in accordance with the local institutional policy.

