3.7.2. Adverse Events

Adverse events (AEs) will be coded to the preferred terms (PT) of the Medical Dictionary for Regulatory Activities (MedDRA®). Summaries for induction period and for the complete study period will be presented separately and by system organ class (SOC), preferred term, and severity and/or relatedness, the number and percentage of subjects for whom events were reported.

Adverse events (AEs) are recorded from signing of the informed consent form through the final follow-up assessment. Adverse events observed prior to first dose are non-treatment emergent.

All summaries will be presented for both the Induction Period and the overall study period separately.

Treatment emergent adverse events are defined as follows for induction period and overall:

- Induction period TEAEs are events with a start date/time after the first dose date/time in Induction period up to the date/time of ATE Day 1 dose or date of last dose of study drug + 28 days, whichever is earlier.
- TEAEs for the whole study and listings are defined as AEs with onset on or after the first initiation of study drug up to the date of last dose study drug + 28 days.

Only treatment-emergent AEs will be summarized in the tables. Separate by-subject listings of all TEAEs and all non-TEAEs will be provided.

An AE will be considered a treatment-emergent serious AE (TESAE) if it is a TEAE that additionally meets any SAE criteria.

If more than 1 AE is coded to the same preferred term for the same subject, the subject will be counted only once for that preferred term using the most severe and most related occurrence for the summarizations by severity and by relationship to study drug.

Summary tables will also be provided for Induction period and overall for subjects with:

- TESAEs by SOC and PT
- TEAEs leading to discontinuation of study drug by SOC and PT
- Drug related TEAEs by SOC and PT
- TEAEs by severity and by SOC and PT
- TEAEs resulting in death by PT

Listings of all AEs, SAEs, and AEs leading to premature study drug discontinuation by subject will be presented.

An overall summary of adverse events will also be presented and will include the following summary lines: Any AE, Moderate or Severe AEs, AEs Related to Study Drug, Moderate or Severe AEs Related to Study Drug, Serious AEs, Serious AEs Related to Study Drug, AEs Leading to Premature Study Drug Discontinuation, AEs Leading to Temporary Interruption of Study Drug, and Deaths During Study.

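### Protocol 7.3.2 sets a reasonable-possibility test for causality, then words Related and Not Related so that some events literally fit neither

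*Protocol*

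**What the plan says.** Protocol 7.3.2 gives this basis for the causality assessment: "clinical judgment regarding the reasonable possibility that the study medication caused the event and may include consideration of some or all of the following factors". The listed factors are alternative causes, timing, consistency with known actions or toxicity, and dechallenge or rechallenge.

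The section then says the relationship "will be described using one of the following categories" and gives two:

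- Not Related: "Evidence exists that the adverse event has an etiology other than the study drug".
- Related: a run of statements. There is a temporal link, the event is not readily explained by the subject's condition or other treatment, and there is a measure of certainty drawn from what the drug is known to do. The run continues: "In case of cessation or reduction of the dose, the event abates or resolves and reappears upon rechallenge".

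There is no third category.

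Four other places bear on this:

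- Protocol 7.1.4 says that, with stated exceptions, "all of these AESIs should lead to discontinuation of the study drug". Section 6.5.1 says the same for non-laboratory AESIs other than non-melanoma skin cancer, and 6.4.21 says it for serious infection.
- Protocol 7.4.3 sets a different phrase for onward reporting: "An SAE may qualify for reporting to regulatory authorities if the SAE is possibly attributable to the study drug", and is also unexpected.
- Protocol 7.4.2 lets investigators report related SAEs for 30 days after the last visit.
- Protocol 8.8.2 plans drug-related AE and drug-related SAE tables. SAP 3.7.2 plans "Drug related TEAEs by SOC and PT" and adds overall-summary lines for related, related moderate or severe, and related serious events. It counts the most related occurrence per preferred term.

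**The concern.** The lead-in and the category definitions are two different tests in one section. Under the lead-in, rechallenge is one thing an investigator may consider. Under the Related definition it reads as part of what has to be true once the drug has been stopped or reduced. Known pharmacology moves in the same way, from an optional factor to an element of the definition. Not Related is not the complement of Related, because it asks for positive evidence of another cause.

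Safety and tolerability is one of the two primary objectives. The investigator's two-way answer feeds every table row labelled drug-related or related. If one site works from the lead-in and another from the definitions, the same clinical picture can be recorded differently, and the rows then mix two standards.

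**Working it through.** The documents give no figure on this point, so there is nothing to recompute. The check is to take the two definitions literally and see which events each one covers.

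| Event | Not Related as worded | Related as worded | Lead-in test |
|---|---|---|---|
| A. Evidence of another cause | Met | Not met | Answerable |
| B. No other cause found, fits known actions, drug continued unchanged | Not met | Met (the cessation sentence is not triggered) | Answerable |
| C. No other cause found, fits known actions, drug stopped, no rechallenge | Not met | Not met (reappearance cannot be seen) | Answerable |
| D. No other cause found, does not fit known actions, whatever happens to dosing | Not met | Not met | Answerable |
| E. No other cause found, fits known actions, drug stopped, resolves and recurs on rechallenge | Not met | Met | Answerable |

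A temporal link is assumed in rows B to E. Rows C and D are the gap.

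**Can row C arise?** Yes, from the protocol's own instructions. Sections 7.1.4, 6.5.1 and 6.4.21 expect study drug to stop for most AESIs and for serious infection. For those events reappearance will usually not be observable, and an event such as a malignancy may not resolve after stopping either. The exceptions lie outside this. They are non-melanoma skin cancer (fully resected, in 7.1.4), mono-dermatomal zoster, and laboratory abnormalities judged not to pose an immediate risk. Section 7.2 also makes the laboratory stops depend on the individual case.

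**Can row D arise?** Yes, though less clearly. Protocol 1.4 states that TD-1473 had not been studied in Crohn's disease. Its list of effects seen with a systemic JAK inhibitor includes infection, cancer and intestinal perforation, but not thromboembolic or cardiovascular events, which are AESIs in 7.1.4. The visible text therefore gives an investigator little known action to point to for those two. Section 1.3 is redacted and the Investigator's Brochure is not to hand, so this is a limited reading.

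**What depends on the answer?**

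- Directly: the drug-related rows in Protocol 8.8.2 and SAP 3.7.2, and the optional 30-day reporting in 7.4.2.
- Not directly: the report from site to sponsor within 24 hours, which 7.4.3 requires for SAEs and AESIs (except non-melanoma skin cancer) whatever the causality. Onward reporting to authorities uses its own, looser phrase. Section 3.5.1 lets the sponsor's drug safety staff unblind cases independently for that purpose.

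**Which way would the error go?** An investigator facing row C or D must still tick one box. A reader who gives weight to the demanding Related wording ticks Not Related, and the drug-related count falls below what the lead-in would give. A reader who gives weight to the Not Related wording finds no evidence of another cause and ticks Related. Undercounting is the likelier direction because Related carries more conditions, but the text does not settle it. Inconsistency between readers follows either way.

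**The case against.** The strongest reply is that this is a drafting inconsistency with limited reach. Most of that stands.

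- The rechallenge sentence is conditional, and the lead-in leaves causality to judgment on some or all of the factors. A reader might infer that no event ending in discontinuation can be called Related. The section does not support that; it contradicts itself rather than imposing a bar.
- A reader might infer that serious events could drop out of expedited reporting. The routes in 7.4.3 and 3.5.1 do not support that either. What is left is narrower: no visible text says how the two-way category maps to the reporting phrase.
- A reader might infer that many serious events, or every event without rechallenge, are unclassifiable. Row B shows the second is wrong, and the documents give no basis for the first.
- The 30-day provision in 7.4.2 is an optional addition. All SAEs are recorded through the last visit whatever the relationship, so it does not narrow earlier reporting.
- Other safeguards exist. A blinded external committee adjudicates thromboembolic and major cardiovascular events (7.3.3). An independent committee reviews unblinded safety data (6.5.3). AESIs, serious TEAEs, discontinuations and deaths are tabulated irrespective of causality (SAP 3.7.2 and 3.7.2.1). Sites are blinded, so in induction the same wording applies to all arms.

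These safeguards protect the overall safety assessment but do not repair the drug-related rows. Nothing visible says that the committee's adjudication replaces the investigator's category in those tables.

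**Conclusion.** The plan is wrong as written, with a confined effect. Section 7.3.2 states one standard and defines its only two categories on others, and the definitions leave a gap that the protocol's own stopping expectations will tend to fill. The consequence is that the drug-related AE and SAE summaries, and the optional 30-day reporting of related SAEs, may be inconsistent between sites and may undercount. The number of events affected cannot be derived from the documents.

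This rests on two assumptions: that at least some sites follow the category wording rather than the lead-in, and that no training or CRF guidance outside these documents has already resolved the conflict.

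It might also be inferred that the SAP should count missing causality as related. That does not follow. Section 7.3 has every AE assessed for relationship, and a forced choice between two boxes produces misclassified answers, not missing ones.

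**What to change.** Replace the two definitions in Protocol 7.3.2 with a complementary pair on the section's own standard:

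- Related: there is a reasonable possibility that the study drug caused the event.
- Not Related: there is no reasonable possibility that the study drug caused the event.

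Keep dechallenge, rechallenge and known pharmacology in the factor list above them, as support for the judgment and not as conditions. Add a sentence to 7.4.3 stating how the category maps to the reporting phrase used there. No dose, visit or stopping instruction needs to change.

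The cost is one paragraph of protocol text and matching CRF completion guidance. Somewhat more events will be called related. If assessments have already been collected under the present wording (the SAP Introduction records a decision to terminate the study early), the study report should say which standard sites applied and caution readers on the drug-related rows.
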